### **11.3.1 Pregnancies**

Pregnancies occurring while the subject is on study drug or within 4 weeks after the subject's last dose of study drug are considered expedited reportable events. If the subject is on study drug the study drug is to be discontinued immediately. The pregnancy must be reported by the Brown University Oncology Research Group within 24 hours of the Investigator's knowledge of the pregnancy by phone and facsimile using the SAE Form.

The Investigator will follow the subject until completion of the pregnancy, and must notify BrUOG of the outcome as specified below. The Investigator will provide this information as a follow-up to the initial SAE. If the outcome of the pregnancy meets the criteria for immediate classification as a SAE (i.e., spontaneous abortion [any congenital anomaly detected in an aborted fetus is to be documented], stillbirth, neonatal death, or congenital anomaly), the Investigator should follow the procedures for reporting SAEs (i.e., report the event to BrUOG by facsimile within 24 hours of the Investigator's knowledge of the event).

Any suspected fetal exposure to Nivolumab must be reported to BrUOG within 24 hours of being made aware of the event. The patient should be referred to an obstetrician/gynecologist experienced in reproductive toxicity for further evaluation and counseling.

All neonatal deaths that occur within 30 days of birth should be reported, without regard to causality, as SAEs. In addition, any infant death after 30 days that the Investigator suspects to be

related to the in utero exposure to the study drug should also be reported. In the case of a live “normal” birth, BrUOG should be advised as soon as the information is available.

If a female partner of a male subject taking investigational product becomes pregnant, the male subject taking IP should notify the Investigator, and the pregnant female partner should be advised to call their healthcare provider immediately.

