D- For patients who are removed from protocol treatment due to toxicity, without progression, Follow-up until disease progression will include CT, disease free and overall survival every 3 months (a month window is allotted for scheduling). CT scans may be done outside of the 3 month window as per MD discretion; however it is suggested that CT scans be done q 3 months. For patients who come off study for progression, overall survival is to be reported every 3 months (a month window is provided). Follow-up will be for 5 years.

E post-menopausal women (surgical menopause or lack of menses  $\geq 12$  months) do not need to have a pregnancy test, document status. If HCG is not drawn, sites are asked to document menopausal status on lab form.

F It is appropriate to use labs from screening for cycle 1 day 1, if labs are within 14 days (pregnancy must be within 7 days as noted above for applicable patients). A physical exam within 7 days prior to cycle 1 day 1 may be utilized. PS, weight, vitals, conmeds, and AE assessment can be used from screening for cycle 1 if assessments are within 14 days of treatment. Labs and physical exam for all subsequent cycles can be within 3 days prior to day 1 of treatment. Another day is provided for holidays.

G Physician note required to be sent. For ablation time points, sites are to submit consult notes from appointment pre-ablation and if consult occurs post ablation that not is also to be sent.

H Adverse event evaluation, inclusive of SAE evaluation, will be done 30 days post last dose of drug (+1 week window). SAEs occurring outside this 30 day window must be reported if the event is considered to be possibly related to the drug, even if patient begins a new treatment. If a patient begins a new treatment, AE evaluation will be stopped unless the patient experiences an event that is thought to be possibly related to the study treatment. It is required to inform BrUOG of patient beginning a new treatment.

I Physical to be done in coordination with 30 day toxicity assessment (+ 1 week allowed). Physical post 30 day assessments not required per study

JCT scans (or disease assessment by MRI or PET) to be completed approximately every 12 weeks (approximately every 6 cycles). For patients staying on study post initial PD – see section 7.3- next scan to confirm PD to be done in 1 month time period if patient remains on study.

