## **11.3 BRUOG ADVERSE EVENT REPORTING REQUIREMENTS**

Investigators are required by Federal Regulation to report adverse drug reactions. Question regarding drugs as used in this study should be directed to the Brown University Oncology Research Group (BrUOG) Central Office, [contact] [contact], which will in turn notify the Principal Investigator.

Intensity for each adverse event will be scored using CTCAE Version 4. A copy of the CTCAE Version 4 can be downloaded from the CTEP homepage (<http://ctep.info.nih.gov>). All appropriate treatment areas have access to a copy of the CTCAE Version 4. All adverse clinical experiences, whether observed by the investigator or reported by the patient, must be recorded, with details about the duration and intensity of each episode, the action taken with respect to the test drug, and the patient's outcome. The investigator must evaluate each adverse experience for its relationship to the test drug and for its seriousness.

AEs and SAEs will be captured and reported from when the patient signs consent to 4 weeks post last dose of drug or until the subject withdraws consent from study participation (declines participation) or at the time patient becomes a screen failure, whichever occurs first.

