### **11.3.2 Serious Adverse Event Reporting Procedures**

All SAEs and pregnancy reports must be reported to the Brown University Oncology Research Group to align with 24 hour notification. For pregnancy reporting time frames see section 11.3.1.

All other initial SAE information and all amendments or additions must be recorded on a MedWatch 3500A SAE form and be faxed or emailed to BrUOG within 5 business days of being made aware of the event. If the SAE is a death thought to be related to the study drug or ablation, deaths must be reported to BrUOG within 24 hours/1 business day of the investigator being made aware of the event.

BrUOG [contact] Email: [[name]\\[contact]](mailto:[contact])  
[[name]\\[contact]](mailto:[contact])

The treating investigator has the obligation to report all serious adverse events to the Brown University Oncology Research Group’s (BrUOG) office who in return will report to the FDA, and all sites participating in the trial.

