### **Expedited Reporting by Investigator to BrUOG**

Serious adverse events (SAE) are defined above. All events must be reported, by FAX or email to the Brown University Oncology Research Group. The initial report must be as complete as possible, including an assessment of the causal relationship between the event and the investigational product(s), if available. Information not available at the time of the initial report (e.g., an end date for the adverse event or laboratory values received after the report) must be documented on a follow-up report. A final report to document discharge is required.

This includes serious, related, labeled (expected) and serious, related, unlabeled (unexpected) adverse experiences. All deaths during treatment or within 30 days following completion of active protocol therapy (drug or ablation) must be reported within 5 business days of when the investigator is made aware of the event or as soon as the investigator is made aware of the event. Deaths that are thought to be related to drug are to be reported to BrUOG in 24 hours/1 business day of being made aware of the event. SAEs occurring within 30 days following completion of active protocol therapy (drug or ablation) will be captured even if patient begins a new treatment. AE evaluation will stop once patient begins a new treatment.

All adverse events and special reporting situations, whether serious or non-serious, related or unrelated, will be reported from the time a signed and dated ICF is obtained until 30 days after the last dose of nivolumab or ablation (whichever is last), or until the subject withdraws consent from study participation (declines participation) or at the time patient becomes a screen failure, whichever occurs first.

Serious adverse events occurring more than 4 weeks after study discontinuation need only be reported if a relationship to the study drug (or therapy/ablation) is suspected.

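### Section 11.3.1 ends automatic pregnancy reporting 4 weeks after the last dose, about a month before the protocol's 2-month contraception period is over

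*Protocol*

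**What the plan says.** Protocol section 11.3.1 sets the rule for pregnancy as such: those arising on study drug or "within 4 weeks after the subject's last dose of study drug are considered expedited reportable events". Section 11.3.2 confirms that this is the governing rule: "For pregnancy reporting time frames see section 11.3.1".

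Section 11.3.1 also contains four provisions with no stated time limit:

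- Suspected exposure: "Any suspected fetal exposure to Nivolumab must be reported to BrUOG within 24 hours of being made aware of the event".
- Neonatal death: "All neonatal deaths that occur within 30 days of birth should be reported, without regard to causality, as SAEs".
- Live normal birth: the coordinating office should be told once the information is available.
- Partner pregnancy: "If a female partner of a male subject taking investigational product becomes pregnant, the male subject taking IP should notify the Investigator". The sentence gives no period after the last dose and no express report by the investigator.

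The surrounding rules on adverse events use similar windows. Section 11.3 says "AEs and SAEs will be captured and reported from when the patient signs consent to 4 weeks post last dose of drug". The expedited-reporting text under 11.3.2 collects adverse events and special reporting situations "until 30 days after the last dose of nivolumab or ablation (whichever is last"). It limits later serious adverse events to those with a suspected relationship. Footnote H of the study calendar says much the same: "SAEs occurring outside this 30 day window must be reported if the event is considered to be possibly related to the drug".

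Contraception runs longer. Criterion 3.1.12 asks men and women of childbearing potential for barrier methods during the study and up to 2 months after. The Appendix B checklist asks for effective contraception on treatment and for at least 2 months afterwards.

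**The concern.** The yardstick is the protocol's own. It asks patients to avoid pregnancy for 2 months, but automatic reporting of a pregnancy stops at 4 weeks. For a pregnancy that begins after that point, initial notification depends on someone suspecting fetal exposure or relatedness.

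The protocol does not say that conception within the contraception period counts as suspected exposure, so two investigators could treat the same day-45 conception differently. Section 11.3.1 also has the investigator send the outcome as a follow-up to the initial report. Without an initial report, that follow-up is not clearly triggered.

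What is at stake is completeness of safety information on a rare event. No efficacy result depends on it.

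**Working it through.** The plan states no figure for this interval, so there is none to reproduce. The check compares texts and counts days.

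**Inputs**

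- Automatic pregnancy window: 4 weeks = 28 days after the last dose of study drug (11.3.1).
- Alternative window: 30 days after the last nivolumab dose or ablation, whichever is later (expedited-reporting text under 11.3.2). It applies only if pregnancy counts as a special reporting situation, a term the protocol does not define.
- Contraception period: 2 months, counted here from the last dose as in the checklist. Assumption: two calendar months, which is 59 to 62 days depending on the start date.
- A pregnancy is placed by when it begins. One that begins by day 28 and is discovered later is already covered.

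**Days not covered automatically = contraception period minus reporting window**

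- 28-day window: 59 − 28 = 31 days; 62 − 28 = 34 days.
- 30-day window: 59 − 30 = 29 days; 62 − 30 = 32 days.

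Across both readings this is 29 to 34 days, roughly the second month after the last dose.

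**What moves the figure**

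- Under the 30-day reading, an ablation after the last dose shortens the interval. For illustration, an ablation 7 days later moves the end of the window to day 37 and leaves 59 − 37 = 22 to 62 − 37 = 25 days.
- Criterion 3.1.12 counts from the course of the study. If that ends after the last dose, the interval is longer. The protocol does not allow this to be quantified.

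**Does another provision close the interval?**

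| Provision | Time limit | Needed to trigger it |
|---|---|---|
| Suspected fetal exposure (11.3.1) | none | suspicion of exposure |
| Late serious adverse event (expedited-reporting text; footnote H) | none stated | a serious event, and a suspected or possible relationship |
| Neonatal death within 30 days of birth (11.3.1) | none stated | that outcome; causality irrelevant |
| Live normal birth (11.3.1) | none stated | that outcome |

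The first provision covers much of the interval. The second would not ordinarily capture an ongoing pregnancy, because pregnancy is not among the serious outcomes listed in section 11.1. The last two concern outcomes and do not clearly require notification of the pregnancy when it becomes known. No provision makes every pregnancy that begins in the interval reportable.

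**The case against.** The best defence has three parts.

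First, nothing in the documents requires the reporting window to equal the contraception period, and 4 weeks is the general adverse-event window of section 11.3. This stands: the plan does not contradict itself here, and the point is about a choice of window.

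Second, the suspected-exposure duty is mandatory, due within 24 hours and open-ended. An investigator who learns of a conception while contraception is still asked for may well have grounds to suspect exposure. This also stands in large part. What remains is a pregnancy in the interval that nobody regards as exposed, and the protocol gives no criterion for that judgement.

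Third, the live-birth and neonatal-death sentences carry no window, so some outcomes could reach the coordinating office without any suspicion. If they stand alone, they require outcome reports at any time. If they belong only to pregnancies already reported, neither helps. On either reading, early notification of the pregnancy itself is not secured.

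On partners, a pregnancy with suspected exposure already falls under the open-ended duty. The consent form is not part of the text available for this review, so any partner wording there could not be checked.

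A reader might go further and infer that pregnancies after day 28 are never reportable, or that outcome follow-up rests wholly on suspicion or a neonatal death. The documents do not support either inference, because of the suspected-exposure and live-birth sentences.

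**Conclusion.** The mismatch is real and minor. Automatic reporting of a pregnancy ends about 29 to 34 days before the 2-month contraception period does. The figure assumes calendar months counted from the last dose and depends on whether the 28-day or the 30-day window applies. Within the interval, initial notification rests on suspected fetal exposure or on a late serious event suspected to be related.

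The figure should not be read as a measure of risk. It counts calendar days, and the documents give no half-life, washout or exposure risk for that period, so it does not show that half of the risk goes unobserved.

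Section 17.1 caps accrual at 33 patients, so few or no affected pregnancies are expected. The response endpoint, the Simon two-stage rules and the error rates do not depend on this provision. The change is worth making for consistency and is not a condition for the trial's validity.

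**What to change.** In section 11.3.1, replace the 4-week limit with 2 months after the subject's last dose of study drug, which is the checklist's starting point. Apply the same window to pregnancies in female partners of male subjects, and state that the investigator reports them to the coordinating office. Keep the suspected-exposure, neonatal-death and live-birth sentences as they are.

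The pregnancy window would then be longer than the general adverse-event window of section 11.3, which is acceptable because 11.3.2 already refers pregnancy timing to 11.3.1. Criterion 3.1.12 would still count from the course of the study; wording it like the checklist would complete the alignment.

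The cost is a wording amendment and at most a few extra reports. No new visit is needed, since section 13.0 and footnote D of the study calendar already provide for five years of follow-up with reports about every 3 months. Sample size, endpoint and analysis do not change.

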### **11.3.2 Serious Adverse Event Reporting Procedures**

All SAEs and pregnancy reports must be reported to the Brown University Oncology Research Group to align with 24 hour notification. For pregnancy reporting time frames see section 11.3.1.

All other initial SAE information and all amendments or additions must be recorded on a MedWatch 3500A SAE form and be faxed or emailed to BrUOG within 5 business days of being made aware of the event. If the SAE is a death thought to be related to the study drug or ablation, deaths must be reported to BrUOG within 24 hours/1 business day of the investigator being made aware of the event.

BrUOG [contact] Email: [[name]\\[contact]](mailto:[contact])  
[[name]\\[contact]](mailto:[contact])

The treating investigator has the obligation to report all serious adverse events to the Brown University Oncology Research Group’s (BrUOG) office who in return will report to the FDA, and all sites participating in the trial.

### **Expedited Reporting by Investigator to BrUOG**

Serious adverse events (SAE) are defined above. All events must be reported, by FAX or email to the Brown University Oncology Research Group. The initial report must be as complete as possible, including an assessment of the causal relationship between the event and the investigational product(s), if available. Information not available at the time of the initial report (e.g., an end date for the adverse event or laboratory values received after the report) must be documented on a follow-up report. A final report to document discharge is required.

This includes serious, related, labeled (expected) and serious, related, unlabeled (unexpected) adverse experiences. All deaths during treatment or within 30 days following completion of active protocol therapy (drug or ablation) must be reported within 5 business days of when the investigator is made aware of the event or as soon as the investigator is made aware of the event. Deaths that are thought to be related to drug are to be reported to BrUOG in 24 hours/1 business day of being made aware of the event. SAEs occurring within 30 days following completion of active protocol therapy (drug or ablation) will be captured even if patient begins a new treatment. AE evaluation will stop once patient begins a new treatment.

All adverse events and special reporting situations, whether serious or non-serious, related or unrelated, will be reported from the time a signed and dated ICF is obtained until 30 days after the last dose of nivolumab or ablation (whichever is last), or until the subject withdraws consent from study participation (declines participation) or at the time patient becomes a screen failure, whichever occurs first.

Serious adverse events occurring more than 4 weeks after study discontinuation need only be reported if a relationship to the study drug (or therapy/ablation) is suspected.

#### **11.4 Assessing Causality:**

Investigators are required to assess whether there is a reasonable possibility that treatment caused or contributed to an adverse event. The following general guidance may be used.

**Yes:** if the temporal relationship of the clinical event to treatment administration makes a causal relationship possible, and other drugs, therapeutic interventions or underlying conditions do not provide a sufficient explanation for the observed event.

**No:** if the temporal relationship of the clinical event to treatment administration makes a causal relationship unlikely, or other drugs, therapeutic interventions or underlying conditions provide a sufficient explanation for the observed event.

#### **11.5 Types of Report:**

**Telephone report:** For SAE's contact BrUOG Central Office at [contact] within 24 hours upon learning of the event for notification and prior to submitting the SAE report.

**Written report:** Send the copy of the Medwatch 3500A within 5 business days of being made aware of the event to the BrUOG Central Office by email, scan or Fax:

Brown University Oncology Research Group

[contact], [contact]

Email: [[name]\\[contact]](mailto:[contact]), [[name]\\[contact]](mailto:[contact])

All deaths during treatment or within 30 days following completion of active protocol therapy (last dose of drug or ablation) must be reported within 5 business days of being made aware of the event or as soon as the investigator is made aware of the event. If the death is thought to be related to the study drug or ablation, deaths must be reported to BrUOG within 24 hours/1 business day of the investigator being made aware of the event. For pregnancies please refer to prior section.

#### **MedWatch 3500A Reporting Guidelines:**

In addition to completing appropriate patient demographic and suspect medication information, the report should include the following information within the Event Description (section 5) of the MedWatch 3500A form:

- Treatment regimen (dosing frequency, combination therapy)
- Protocol description (and number, if assigned)
- **Description of event, severity, treatment, and outcome, if known**
- Supportive laboratory results and diagnostics
- Investigator's assessment of the relationship of the adverse event to each investigational product and suspect medication
- Must type SAEs

#### **Follow-up information: \*Follow-up SAEs are required to document patient discharge or resolution of SAE event\***

Additional Info maybe added to a previously submitted report by any of the following methods.

- Adding to the original MedWatch 3500A and submitting it as follow-up
- Adding supplemental summary information and submitting it as follow-up with the original MedWatch 3500A form

Summarizing new information and faxing it with a cover letter including subject identifiers (i.e. D.O.B. initial, subject number), protocol description and number, if assigned, suspect drug, brief adverse event description, and notation that additional or follow-up information is being submitted (The subject identifiers are important so that the new information is added to the correct initial report).

#### **11.6 BrUOG Responsibility Regarding Reporting:**

The BrUOG Central Office will notify by phone and/or fax all drug reaction reports to the FDA, the Principal Investigator, and the participating sites (who will in turn notify their local IRBs) as soon as possible but no later than 7 calendar days after the initial receipt of the information. A copy of the form will be kept by the BrUOG Central Office.

**Fax: [name] ([name]) For IND exempt study or for IND study the SAE will be sent to FDA Division fax line that has responsibility for review of IND)**

**Mail: For IND studies BrUOG will send the SAE as an amendment to the IND as well**

#### **11.7 Safety Reporting for IND Holders**

In accordance with 21 CFR 212.32, Sponsor-Investigator of the study conducted under an IND must comply with following safety-reporting requirements:

